## STUDY TIMELINE

This is a dose escalation trial. We expect to complete the study within four months. Each eligible subject's participation in the study will be approximately four weeks. Primary analyses are expected to be completed within a month of the study completion.

## STUDY ENDPOINTS

Eligible subjects will consume each dose of soy for one week. They will report any adverse events and complete a tolerability questionnaire. Our primary aim is to determine the maximum tolerated dose. The secondary outcome will be the change in fecal SCFA with each escalating dose.

## RESEARCH DESIGN AND METHODS

To determine an acceptable dose of DF, we will conduct a dose escalation trial in eight elderly subjects with obesity and test the tolerability to soft foods containing 4 g, 8 g, and 12 g of DF/day from soy for one week at each dose. The soy contains approximately 39% DF. Therefore, subjects will consume soft foods containing 10 g, 20 g, and 30 g of soy/day to provide the required DF doses and the phytonutrients in soy. This clinical trial is patterned according to the National Cancer Institute's (NCI's) recommendation for dose escalation to determine toxicity to a drug. We are testing a food, and we know that relatively large doses of DF are tolerated if daily intake is divided into small portions throughout the day. However, we will evaluate tolerability to DF from soy, and measure fecal SCFA as a biomarker of compliance with the intervention. The maximum recommended starting dose (MRSD) for DF may be estimated at 4 g which added to average DF intake in the US of approximately 17g is not in excess of the recommended adequate intake of 25 - 38 g/day. The dose escalation scheme recommended for first-in-human trials is rapid dose escalation initially (MRSD x 2) until the estimated desirable dose (8 g) is reached and then at a more cautious escalation (e.g. MRSD x 1.5). Subjects will consume soft foods containing 4 g/day of DF from soy for one week, then proceed to 8 g/day for one week, followed by 12 g/day for one week, incorporated into their usual diet.

Adverse events will be recorded as they occur and collated for each week. Fecal SCFA and gastrointestinal (GI) symptoms will be evaluated at the end of each week (Figure 2).

[figure not shown]

Figure 2. Study schema

## Study Subjects

This study will enroll 10 healthy adult male and female subjects. Subjects will be enrolled on the basis of the following eligibility criteria:

### Inclusion Criteria

- Adult (70 - 85 years).
- Body mass index between 30 and 40 kg/m^2.
- No evidence of diabetes (fasting blood sugar <126 mg/dL).
- No evidence of dementia (MMSE score > 25).

- No evidence of depression (Geriatric Depression Scale-15 [GDS-15] < 6).
- Are weight stable (< 3 kg weight change in the past three months).

#### Exclusion Criteria

Subjects will not be eligible for participation if they meet one or more of the following exclusion criteria:

- Have type 1 or type 2 diabetes.
- Had diagnosis of cancer (within the last five years).
- Report advanced disease of any major organs.
- Report clinically significant gastrointestinal malabsorption syndromes such as chronic diarrhea, or celiac disease.
- Have serum triglyceride concentrations > 400 mg/dl.
- Clinically significant abnormal laboratory markers (as determined by the medical investigator).
- Subjects with anticipated surgery during the study period.
- Subjects with a reported history of substance abuse or alcoholism or significant psychiatric disorder that would interfere with the ability to complete the study.
- Subjects who are current smokers or have smoked within the previous three months. Smoking is not permitted during the study.
- Subjects who are unable to provide a baseline blood or fecal sample or if they have any condition that impedes testing of the study hypothesis or makes it unsafe to consume the food being tested in the study (determined by the investigative team).
- Women on hormone replacement therapy unless weight has been stable over the last six months.

**Recruitment.** Subjects will be recruited through the use of printed material, targeted solicitation through the Pennington Biomedical Research Center (PBRC) email listserv and social media. Participants will complete an online screening and will be contacted by a PBRC recruiter for a brief telephone interview to assess eligibility criteria, prior to being scheduled for a clinic visit. Participation will also be solicited with the help of the LA CATS Center community advisory board. Subject eligibility criteria will be evaluated at a single screening visit. The screening visit will occur in the outpatient clinic, in the morning following confirmation of an overnight (at least ten hours) fast. Subjects who provide informed consent will proceed with the tests and measurements of the screening visit. Subjects who satisfy the eligibility criteria will be enrolled in the study. The schedule of assessments is provided in Table 1.

#### **CLINIC VISITS**

Subjects will complete one screening visit. There will be four study visits **unless a participant is intolerant to a dose and cannot be advanced to the next higher dose.**

#### **Screening Visit (2 hours)**

Subjects will report to Pennington Biomedical in the morning following an overnight fast (except for water) that began no later than 10 hours prior to the study appointment. The screening visit includes explanation of the study purpose, procedures, and signing of the informed consent. If the participant agrees to participate by signing a consent form, the following tests and measurements will be performed:

- Self-report of personal and family medical history.
- Blood draw for CBC/Chemistry 15 panel.
- Height, weight, vital signs (blood pressure, pulse, and temperature).
- Concomitant medication use.

- Questionnaires (GDS-15 and MMSE).

Eligible subjects will be contacted by a coordinator to schedule the baseline visit. Subjects will collect a stool collection kit from the coordinator before the baseline visit.

**Table 1. Schedule of Assessments for Dose Response Study**

Procedure	Screening 1	Baseline	Visit 1	Visit 2	Visit 3
PBRC Outpatient Unit					
Infomed Consent	X				
Height	X				
Weight, and Vital Signs	X	X	X	X	X
Chemistry 15 Panel/CBC	X				X*
Medical History Questionnaire	X				
MMSE and GDS-15	X				
Adverse Events**			X	X	X
Medications	X	X	X	X	X
Tolerability Questionnaire**		X	X	X	X
Food Dispensation		X	X	X	
Nutrition Counseling**		X	X	X	
Compliance with Study Foods			X	X	X
Fecal Sample (SCFA)***		X	X	X	X
Fecal Sample (Archives)	X	X	X	X	

\* Or at a prior visit if the dose is not tolerated

\*\* By phone call on day prior to the study visit.

\*\*\*Measured at Scioto Biosciences

### **Baseline (1 hour)**

Subjects will report to the clinic for the visit. The following tests and measurements will be performed:

- Collection of fecal sample.
- Measurement of weight and vital signs.
- Recording of medications.
- Dispensation of study foods.
- Nutrition counseling.
- Completion of tolerability questionnaire.
- Dispensation of stool collection kit.

### **Visit 1 (Week 1, 1 hour)**

Assessment of adverse events, completion of the tolerability questionnaire, and nutrition counseling will be completed by phone on the day prior to the visit to avoid unnecessary food preparations in the event that the participant does not tolerate the dose. Subjects will report to the clinic for the visit and the following tests and measurements will be performed:

- Collection of fecal sample.
- Measurement of weight and vital signs.
- Recording of changes in medications.
- Dispensation of study foods.
- Assessment of compliance by metabolic kitchen staff.

- Dispensation of stool collection kit.

A blood draw for CBC/Chemistry panel will be performed if participants are not being advanced to the next dose. Participants will be advised to report after a ten hour fast.

### **Visit 2 (Week 2, 1 hour)**

Assessment of adverse events, completion of the tolerability questionnaire, and nutrition counseling will be completed by phone on the day prior to the visit. Subjects will report to the clinic for the visit and the following tests and measurements will be performed:

- Collection of fecal sample.
- Measurement of weight and vital signs.
- Recording of changes in medications.
- Dispensation of study foods.
- Assessment of compliance by metabolic kitchen staff.
- Dispensation of stool collection kit.

A blood draw for CBC/Chemistry panel will be performed if participants are not being advanced to the next dose. Participants will be advised to report after a ten hour fast.

### **Visit 3 (Week 3, 1 hour)**

Assessment of adverse events and completion of the tolerability questionnaire will be completed by phone on the day prior to the visit. Subjects will report to the clinic in the morning following an overnight fast (except for water) that began no later than 10 hours prior to the study appointment and the following tests and measurements will be performed:

- Collection of fecal sample.
- Measurement of weight and vital signs.
- Recording of changes in medications.
- Blood draw for CBC/Chemistry 15 panel.
- Assessment of compliance by metabolic kitchen staff.

## **STUDY PROCEDURES**

**Whole soy pods (soy).** The plants will be grown under carefully monitored conditions at the LSU Agricultural Center and harvested at reproductive stage six or when the green pods contain soybeans that fill the pods. The whole pods will be processed at the United States Department of Agriculture (USDA, New Orleans, LA), Food Processing and Sensory Quality Research Unit, where scientists work with foods for research purposes. Slicing the pods into thin cross-sections injures plant cells and activates the synthesis of an anti-microbial compound (glyceollin) synthesized by the plant *de novo* in response to stress. Glyceollins have been shown to improve insulin sensitivity and cognition. The sliced pods will be lyophilized and milled. Nutrient analysis, will be performed at Eurofins Food Chemistry Testing (Madison, WI) using methods of analysis of the Association of Official Analytical Chemists.

**Food Development.** The soy will be incorporated in foods and prepared by the PBRC metabolic kitchen. The PBRC metabolic kitchen is staffed with research dietitians who have a primary responsibility to develop foods for research purposes, plan diets, and execute their delivery. In addition, the applicant is a registered dietitian with experience in food development across cuisines and cultures.

**Nutrition Counseling.** Subjects will be counseled by the study dietitian who will interview the subject in order to assess the subject's current intake. Based on this information, subjects will be counseled on incorporating the test foods in their diet. We expect that subjects will experience GI symptoms from increased DF intake, but from the applicant's practice as a

registered dietitian and evidence in the literature we know that these symptoms resolve. To enhance compliance with the protocol, subjects will receive counseling on managing GI symptoms.

**Food Tolerability.** Subjects will complete a version of the GI symptoms questionnaire designed as a validated assessment for dyspepsia, and modified to make it specific by only including the symptoms that may be experienced with high DF intake. The scale is ranked as none, mild, moderate, and severe for each of four GI symptoms (bloating, abdominal rumbling, flatulence, and abdominal pain). Additionally, subjects will report their stool frequency ranging from 0 to 9+, and stool consistency based on the Bristol Stool scale.

**Blood and Fecal Assessments.** Chemistry 15 panel and CBC, measurements will be performed according to standard PBRC procedures for blood draws and the relevant measurement. The total amount of blood that will be drawn across the study is approximately 20 ml. Homogenized fecal samples will be analyzed for SCFA as previously described.

**MMSE.** A cut-off score of 25 on the MMSE administered at screening will be used to exclude subjects with dementia.

**GDS-15.** The Geriatric Depression Scale is validated for evaluating symptoms of apathy and depression, and will be used as a screening tool. A score > 6 on the GDS-15 has been shown to effectively screen for depression.

## **SAMPLE SIZE AND ANALYSIS**

The primary objective of the study is to determine the maximum tolerated dose of DF. Six subjects at each dose are sufficient to detect tolerability. However, we will enroll 10 subjects to test each dose of DF from soy. Dose safety will be investigated by compiling by treatment (e.g. 4 g dose, 8 g dose, 12 g dose) a list of adverse events such as frequency of headaches, nausea, vomiting. For GI symptoms the scale is ranked as none (no symptoms), mild, moderate, and severe for each of four GI symptoms and the assessment of intensity is provided in the data safety monitoring plan. Moderate and severe ratings will be considered intolerance to the dose. Stool frequency of one to three/day, or three times/ per week is considered regular. Therefore, stool frequency of less than one and more than nine over a 72 hour period will be a consideration for determining intolerance. Stool consistency of Type three to five on the Bristol Stool Scale is considered normal. Any other rating will be considered in the determination of intolerance. To be considered intolerance, subjects must rate stool frequency and consistency as being of moderate to severe intensity.

According to the NCI convention for dose limiting toxicity to a drug, 1) if two out of three (66%) subjects are intolerant to the dose, the next lower dose is the maximum dose tested; and 2) if one out of three (33%) are intolerant to a dose, then that dose is considered the maximum tolerated dose. Therefore for a food, 1) if five out of eight (63%) are intolerant, we will adopt the next lower dose; and 2) if three out of eight (37%) are intolerant to a dose, then that dose will be taken as the maximum tolerated dose.

A mixed effect linear model will be used to estimate changes in the fecal SCFA while accounting for subject correlation across time using all available data. The outcome will be within subject changes over time.

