#### **Study Design**

We propose to conduct a dose escalation trial. We will test the tolerability to 10 g, 20 g, and 30 g of soy containing 4 g, 8 g, and 12 g of DF respectively. At each dose, eight subjects will incorporate the foods into their usual diet for one week. We will evaluate tolerability to each dose and measure fecal SCFA as a biomarker of compliance. Subjects who satisfy the eligibility criteria and express willingness to consume the study foods will be enrolled.

At baseline, weight and vital signs will be measured. Subjects will provide a stool sample collected within the last 48 hours and frozen in containers provided for the purpose. Part of the fecal samples will be archived for future analysis. The study dietitian will interview each subject in order to assess the subject's current intake. Based on this information, subjects will be counseled on incorporating the study foods in their diet with the appropriate fluid intake. Subjects will receive the study foods containing 4g DF/10g soy/day for one week and complete a tolerability questionnaire.

Subjects will consume the soft foods containing soy along with their regular diet for one week, and will be advised to return all used and unused containers at the end of the week. Compliance will be assessed from an interview with the subject and an evaluation of used and unused containers returned by subjects. Pre-intervention tests and measures will be repeated, and adverse events will be recorded. If a dose is tolerated, subjects will receive the next escalated dose for one week (8 g DF/20 g soy/day or 12 g DF/30 g soy/day). At the end of each subject's participation in the study, a fasting blood sample will be drawn for evaluation of CBC, and blood chemistry panel as safety markers.

The results of the present study will guide the design and implementation of a clinical trial to determine the effect of a low GI D+E program on insulin sensitivity and apathy in elderly subjects with obesity and insulin resistance. These results will be significant, in that they will potentially provide a cost-effective intervention that will substantially improve the health and quality of life for the growing number of elderly individuals with obesity who have developed insulin resistance and apathy.

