## HYPOTHESIS AND SPECIFIC AIMS

Edamame or green soybean in the pod has approximately four times more dietary fiber than soybean without the pod. The whole soy pod (soy), rich in phytonutrients, increases fecal fat and glucose excretion and the synthesis of short chain fatty acids in mice. The majority of the clinical and epidemiologic evidence supports the anti-depressive effects of diets high in soybeans. In previous controlled feeding and exercise studies, we found that a low GI D+E for one week (n = 32) or 12 weeks (n = 22) increases insulin sensitivity in older adults with obesity. These data form the basis of a proposal to test the hypothesis that insulin sensitivity mediates apathy in depression. No study to date has empirically tested this hypothesis. The success of the efficacy trial depends on a determination of the optimal dose of dietary fiber from soy that will be tolerated by the elderly. Therefore, the present study will determine the maximum tolerated dose of dietary fiber from soy. The results will inform the development of a randomized controlled trial (RCT) to test the efficacy of a low GI D+E program (with and without soy) to increase insulin sensitivity and reduce apathy in the elderly.

**Aim.** Determine the maximum tolerated dose of dietary fiber from soy in elderly subjects with obesity. This aim requires a dose escalation trial in the elderly with obesity. We will test the tolerability to soft foods including 10 g, 20 g, and 30 g of soy containing 4 g, 8 g, and 12 g of dietary fiber, respectively. At each dose, eight subjects will consume the foods for one week. We will evaluate tolerability to each dose and measure fecal short chain fatty acids as a biomarker of compliance with the intervention.

**Hypothesis:** Since this is a dose finding study there is no hypothesis for the maximum tolerated dose; however, fecal short chain fatty acids will increase with the dose.

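### The number stated for each dose (10, elsewhere eight) is only a maximum at 8 g and 12 g, because intolerant subjects are not advanced and no replacement is stated

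*Combined protocol and SAP*

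**What the plan says.** **Number per dose.** SAMPLE SIZE AND ANALYSIS says "Six subjects at each dose are sufficient to detect tolerability", supported by citation and not by calculation, and then "we will enroll 10 subjects to test each dose of DF from soy". Study Subjects gives the same total: "This study will enroll 10 healthy adult male and female subjects". The abstract (Study Design) differs: "At each dose, eight subjects will incorporate the foods into their usual diet for one week". So does HYPOTHESIS AND SPECIFIC AIMS: "At each dose, eight subjects will consume the foods for one week". The data safety monitoring plan in the appendix also describes eight subjects, and the decision rule for the maximum tolerated dose (MTD) is written in eighths.

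**One cohort.** RESEARCH DESIGN AND METHODS says "we will conduct a dose escalation trial in eight elderly subjects with obesity" and takes those subjects through the three doses one week at a time. There are no separate groups per dose.

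**Who goes on.** CLINIC VISITS plans four study visits "unless a participant is intolerant to a dose and cannot be advanced to the next higher dose". The footnote to Table 1 and the text for Visits 1 and 2 provide an exit blood draw for subjects who are not advanced. STUDY ENDPOINTS, in contrast, says without condition "Eligible subjects will consume each dose of soy for one week".

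No section describes replacing a subject who is not advanced, makes an allowance for attrition, or restates the number for the later doses.

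**The concern.** A fixed number at every dose and a rule that keeps intolerant subjects from the next dose cannot both hold once one subject is intolerant. The stated number then describes who starts 4 g, not who tests 8 g or 12 g.

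The primary aim is the MTD, and it feeds the design of a later randomised trial. The highest dose would have the fewest subjects, all selected for having tolerated the lower doses. The planned lists of adverse events by dose are also hard to read if the number dosed falls from one dose to the next and is not shown beside them.

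**Working it through.** **Is there a figure to reproduce?** No. The plan gives no error rate, power or expected intolerance rate. Six rests on citations and 10 is chosen. What can be checked is whether the described flow delivers the stated number at each dose.

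**Inputs from the plan.** Starters n = 10 or n = 8; one cohort; two steps before 12 g (leaving 4 g and leaving 8 g); no replacement stated.

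**Assumptions.** Each subject exits with probability p at each step, independently, with the same p at both steps and no other dropout. The plan gives no p, so 10%, 20% and 30% are shown as a range.

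**Formulas.**
- Number at 8 g ~ Binomial(n, 1 − p), with mean n(1 − p).
- Number at 12 g ~ Binomial(n, (1 − p)²), with mean n(1 − p)².
- P(full number at 12 g) = (1 − p)^(2n).
- P(fewer than six at 12 g) = the sum over k = 0 to 5 of C(n, k) s^k (1 − s)^(n − k), with s = (1 − p)².

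Example for n = 10 and p = 0.20: s = 0.8 × 0.8 = 0.64; mean = 10 × 0.64 = 6.4; P(all 10) = 0.64^10 = 1%; P(fewer than six) = 27%.

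| Starters | Exit per step | Expected at 8 g | Expected at 12 g | P(full number at 12 g) | P(fewer than six at 12 g) |
|---|---|---|---|---|---|
| 10 | 10% | 9.0 | 8.1 | 12% | 3% |
| 10 | 20% | 8.0 | 6.4 | 1% | 27% |
| 10 | 30% | 7.0 | 4.9 | 0.1% | 65% |
| 8 | 10% | 7.2 | 6.5 | 19% | 18% |
| 8 | 20% | 6.4 | 5.1 | 3% | 60% |
| 8 | 30% | 5.6 | 3.9 | 0.3% | 87% |

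Fewer than six at 12 g becomes more likely than not at about 26% exit per step from 10 starters, and at about 18% from eight.

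**Adding a cohort rule.** The plan takes a dose as the MTD when three of eight are intolerant, and section 3.2 of the data safety monitoring plan has the PI and the Safety Officer discuss whether to escalate. To reflect this, suppose the cohort moves up only when under 3/8 of those dosed are intolerant. Applying 3/8 as a proportion is an assumption, because the rule is written for eight subjects only. Results given that 12 g is reached:

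| Starters | Exit per step | P(12 g reached) | Expected at 12 g, if reached | P(fewer than six), if reached |
|---|---|---|---|---|
| 10 | 10% | 97% | 8.19 | 0.7% |
| 10 | 20% | 75% | 7.01 | 7% |
| 10 | 30% | 41% | 6.32 | 21% |
| 8 | 10% | 93% | 6.63 | 12% |
| 8 | 20% | 68% | 5.75 | 41% |
| 8 | 30% | 38% | 5.18 | 65% |

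Under this rule the fewest possible at 12 g is five from 10 starters (3 of 10 exit, then 2 of 7) and four from eight (2 of 8, then 2 of 6). Falling below six is less likely but still possible.

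**Why the denominator matters.** Assume 10 starters, 20% exit per step and the same 25% weekly event risk at every dose. The expected numbers with an event are 0.25 × 10 = 2.5 at 4 g, 0.25 × 8 = 2.0 at 8 g and 0.25 × 6.4 = 1.6 at 12 g. The counts fall although the risk is constant.

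**The case against.** Most of the opposing case concerns size, and much of it stands.

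- **A reader might infer that 12 g will often rest on fewer than six subjects.** The documents do not support this. They give no intolerance rate, and section 1.1 of the data safety monitoring plan expects all three amounts to be tolerated. From 10 starters the unconditional chance is 3% at 10% exit per step.
- **Paths with much intolerance may never reach 12 g.** This is right, and the second table is the fairer one if the cohort rule is applied as assumed. From 10 starters the expected number at 12 g then stays above six across the range. The result depends heavily on whether 10 or eight start.
- **The flow is disclosed.** Several sections make the next dose conditional on tolerating the present one, and enrolling 10 when six are called sufficient leaves a margin of four. The plan does not present that margin as an allowance for exits, and the sentence on size still says 10 for each dose.
- **The fecal short chain fatty acid (SCFA) analysis copes with early exits.** The mixed model retains every available measurement, so subjects with fewer doses still contribute. This stands.
- **Nothing says raw adverse event counts would be compared across doses.** This is also right. The plan only compiles lists by dose and does not rule out showing the number dosed. The falling counts above show why the denominator should be stated; they do not show an error in the plan.
- **STUDY ENDPOINTS gives no number.** Correct. Its conflict with CLINIC VISITS is over whether every subject receives every dose.

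What remains is the contradiction between a fixed number per dose and non-advancement without stated replacement. None of these points removes it.

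**Conclusion.** The point holds as an inconsistency in the stated size. The 10 (or eight) per dose is a maximum at 8 g and 12 g. It is met if no subject is intolerant earlier and missed as soon as one is, so a shortfall is not certain.

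Whether the number at 12 g drops below six depends on the intolerance rate and on the number of starters. For 10% to 30% exit per step, the chance is 3% to 65% from 10 starters and 18% to 87% from eight. Given that 12 g is reached under the assumed 3/8 rule, it is 0.7% to 21% and 12% to 65%. These figures rest on assumed rates, equal at both steps, independent subjects and no other dropout; further dropout would lower the numbers. They support possible shortfall below six, not frequent shortfall.

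No calculation in the plan fails. The statement of size needs correcting because it describes numbers that the design delivers at the upper doses only in the best case.

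**What to change.** 1. Reconcile 10 with eight throughout, including the denominator of the MTD rule.
2. In the abstract's Study Design, HYPOTHESIS AND SPECIFIC AIMS, and SAMPLE SIZE AND ANALYSIS, state that this number starts 4 g and that the number tested at 8 g and at 12 g is those advanced from the previous dose. Give the expected numbers over a range of exit rates, labelled as assumptions, and say whether a cohort rule for escalation is included.
3. Make STUDY ENDPOINTS consistent with CLINIC VISITS, so that it no longer implies that every subject receives every dose.
4. Report tolerability and adverse events at each dose with the number actually dosed as denominator. Exact confidence intervals would help the reader but are a reporting preference.

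The cost is wording only. No added enrolment is needed and no dose or clinical rule changes. The stated size at 8 g and 12 g becomes less favourable.
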